- 1) Inactivated influenza vaccine recipient controls who received the current IIV formulation (trivalent or quadrivalent) but not Q/LAIV for the season at a Kaiser health maintenance organization (HMO) during the same month that the reference Q/LAIV recipient was vaccinated will be identified and matched based on age (year) and medical center relative to concurrent reference Q/LAIV recipients, using frequency matching. For children 2 to 4 years of age, matching by age will be based on calendar quarter of birth rather than year. Factors such as gender and prior health care utilization level will be included as covariates in the proposed Cox proportional hazards model.
- 2) Unvaccinated controls who did not receive any influenza vaccine for the season will be identified and matched based on age (year) and medical center relative to concurrent reference Q/LAIV recipients using frequency matching. For children 2 to 4 years of age, matching by age will be based on calendar quarter of birth rather than year. Factors such as gender and prior health care utilization level will be included as covariates in the proposed Cox proportional hazards model. Unvaccinated controls will be followed from the date of vaccination of the reference Q/LAIV recipient (the index date).

Health care utilization levels will be defined as “high” ( $\geq 2$  visits to a Kaiser HMO within the 6 months prior to the date of vaccination of the reference Q/LAIV vaccinee) or “low” ( $\leq 1$  visit).

The study is expected to begin in the fall of 2013 following the launch of Q/LAIV and to be completed in a single influenza season. However, if fewer than 10,000 Q/LAIV recipients 2 through 8 years of age are identified following the 2013-2014 influenza season, the study will be continued for additional seasons until enrollment of 10,000 Q/LAIV recipients is completed. A detailed description of safety follow-up is described in Section 11. Data will be collected on subjects for 180 days following vaccination (or the index date for unvaccinated controls).

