## 9.7.3 Planned Analyses

Tabular summaries will be presented by treatment group. Categorical data will be summarized by the number and percentage of subjects in each category. Continuous variables will be summarized by descriptive statistics, including mean, standard deviation, median, minimum, and maximum. The age, gender, medical center, and prior year health care utilization level of the Q/LAIV and control groups will be summarized for descriptive purposes. Race information is not available in the Kaiser HMO databases.

Rates of events will be presented per 1,000 person-years. All statistical tests will be 2-sided and performed at the significance level of 0.05. Due to the exploratory nature of the study and the lack of formal hypothesis testing, multiple CIs will be constructed in the primary analysis without multiplicity adjustment. Due to the large number of unadjusted CIs to be evaluated, it is expected by chance alone that a number of CIs will not include one and suggest higher or lower event rates in the Q/LAIV group. Therefore, further statistical and medical assessments may be performed for events with observed increases that are statistically significant and/or medically important.

Incidence rates of adverse events of interest during periods at risk after Q/LAIV vaccination will be compared to incidence rates during reference periods later in the follow-up as presented in [Table 9.3-1](#) (within-cohort analysis) and to incidence rates in controls (matched unvaccinated subjects and matched IIV recipients).

Incidence rates will be reported as subjects with an event per 1,000 person-years. If a subject has more than one event in the analysis window, the subject will be counted only once for the analysis. Relative risks (RR) and corresponding 95% CIs will be constructed for each event for safety comparisons with control groups. Crude RR and adjusted hazard ratio (HR) and corresponding 95% CIs for each event will be derived:

- Crude RR and exact 95% CI will be calculated without adjustment of any covariate.
- Adjusted HR and corresponding 95% CI will be obtained using Cox proportional hazards model with calendar time data input adjusting for seasonal changes in

background rates and other confounders. This multivariable analysis is detailed in Section 9.7.4.

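### Control groups are defined by vaccine status over the whole season, including time after follow-up starts, so the control comparisons can be biased if an event changes later vaccination

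*Protocol*

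**What the plan says.** Section 9.1 describes the two control groups.

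- **Unvaccinated group.** Its entry condition covers the season: "Unvaccinated controls who did not receive any influenza vaccine for the season will be identified". Its follow-up starts at a date inside that season: "Unvaccinated controls will be followed from the date of vaccination of the reference Q/LAIV recipient (the index date"). The length is then fixed: "Data will be collected on subjects for 180 days following vaccination (or the index date for unvaccinated controls").
- **IIV group.** It consists of members "who received the current IIV formulation (trivalent or quadrivalent) but not Q/LAIV for the season", vaccinated "during the same month that the reference Q/LAIV recipient was vaccinated".

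The protocol has no rule that keeps a member who is unvaccinated at the index date and censors that member at a later influenza vaccination. It also states no mirror condition for Q/LAIV recipients who later receive IIV.

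Prior utilization is a covariate in the Cox model. Section 9.1 counts "visits to a Kaiser HMO within the 6 months prior to the date of vaccination of the reference Q/LAIV vaccinee". Section 9.7.3 lists, among descriptive characteristics, the "prior year health care utilization level of the Q/LAIV and control groups".

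**The concern.** A cohort member should be classified from what is known when follow-up starts. Here a member unvaccinated on an October index date but vaccinated in December is removed retroactively, together with the October and November follow-up. That is harmless if later vaccination has nothing to do with events. It is not harmless if the two are linked, and a link is plausible in both directions. A clinic visit for an event is an opportunity to vaccinate, which removes controls with events and lowers the control rate. Illness can also put vaccination off, which retains controls with events and raises the control rate.

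The first direction creates a false safety signal. The second hides a real one, which matters more in a safety study. Section 8 makes the control comparisons part of the stated objective. For narcolepsy/cataplexy they are the only comparison, because Table 9.3-1 gives no reference period for that event.

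**Working it through.** **1. The plan's own figure.** Section 9.5 claims about 90% power for a relative risk (RR) of 1.5 with 10,000 children and an event in 1 in 100 of the comparison group. Assuming equal groups, with two-sided alpha of 0.05:

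z = (0.015 − 0.010) / √[(0.015×0.985 + 0.010×0.990)/10,000] = 0.005/0.001571 = 3.18; power = Φ(3.18 − 1.96) = 88.9%.

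The stated power reproduces and is not in dispute. It assumes an unbiased control risk.

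**2. Can the planned model repair the selection?** Section 9.7.4 uses calendar-time risk sets, so each event is compared with those under observation at that time. A member removed for a later vaccination is missing from every earlier risk set. Covariates and calendar time cannot put that member back. Sections 9.1 and 9.9 acknowledge baseline differences and indication bias, but not selection on vaccination after the index date.

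**3. Size of the bias when the true RR is 1.** Inputs:

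- p = 0.01, the comparison-group risk in Section 9.5.
- v0 = probability of later vaccination without an event; v1 = the same with an event. Neither is in the protocol, so both are assumptions.

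Control risk after selection = p(1 − v1) / [p(1 − v1) + (1 − p)(1 − v0)]. Dividing p by this gives

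RR read = [p(1 − v1) + (1 − p)(1 − v0)] / (1 − v1).

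Example with v0 = 20%, v1 = 10%: (0.01×0.90 + 0.99×0.80)/0.90 = 0.801/0.90 = 0.89. With v1 = 30%: (0.007 + 0.792)/0.70 = 1.14.

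| v0 | v1 = 0.5 v0 | v1 = v0 | v1 = 1.5 v0 |
|---|---|---|---|
| 10% | 0.95 | 1.00 | 1.06 |
| 20% | 0.89 | 1.00 | 1.14 |
| 30% | 0.83 | 1.00 | 1.27 |

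The same formula applies to the IIV group if v0 and v1 mean later receipt of Q/LAIV. No rate for that is given either.

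**4. What such a shift does to inference** (10,000 per group, 1% risk in the Q/LAIV group):

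- Spurious RR 1.10: events 100 and 90.9; SE of log RR = √(1/100 + 1/90.9) = 0.145; ln 1.10/0.145 = 0.66; chance of a false significant increase = 1 − Φ(1.96 − 0.66) ≈ 10%, against 2.5% without bias.
- Spurious RR 0.90: events 100 and 111.1; SE = 0.138; ln 0.90/0.138 = −0.76; chance of a false significant decrease = Φ(−1.96 + 0.76) ≈ 12%.

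**5. Utilization window.** For unvaccinated controls the reference recipient's date is their index date, so the window contains no follow-up days. An IIV control vaccinated earlier in the month than the reference recipient can have some. With dates assumed uniform over a 30-day month, the reference date is later in 435/900 = 48% of pairs, by 31/3 = 10.3 days on average. The window then covers 44% of IIV risk days 0–3, 28% of days 1–14 and 11% of days 1–42. An outcome visit can move a control from low to high utilization only if that person had exactly one other visit. With Poisson prior visits (mean 0.5 to 4), stratum-specific RRs shift, but the pooled utilization-adjusted RR stays between 1.000 and 1.002.

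**The case against.** The strongest reply is that every non-null figure in the table comes from assumed inputs. If an event does not alter later vaccination, the bias is exactly zero. The formula also lets an event affect all later vaccination in the season, whereas a vaccination that precedes the event cannot be caused or deferred by it; most risk windows are only 0–3 or 1–42 days. The study is declared hypothesis generating, the within-cohort analysis uses no controls, and Section 9.7.3 foresees further assessment of observed increases. All of this stands and limits the size of the claim. It does not remove the selection rule, and a follow-up look at increases would not catch a masked one.

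A reader might infer three stronger things that the documents do not support.

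- **That the control rates are certainly distorted.** The protocol has no data on later vaccination, so only the possibility, in either direction, follows from the text.
- **That the utilization covariate also selects controls on the outcome, or adjusts the outcome away.** Utilization is neither a matching nor an entry factor, so it cannot change who is a control or any crude rate. Step 5 shows a negligible effect on the pooled estimate.
- **That the protocol gives two competing definitions of the model covariate.** The prior-year wording is in a descriptive summary; Section 9.1 holds the operational definition. This is a matter of wording.

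How index dates are allocated under frequency matching is a specification commonly left to the analysis plan and is not counted here.

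**Conclusion.** The point holds in a limited form. Followed as written, Section 9.1 selects unvaccinated controls, and in parallel IIV controls, partly on vaccination after follow-up starts. This can bias both control comparisons. The direction is unknown. The size depends on rates the protocol does not give: within about 5% or 6% of the null at 10% later vaccination, and 0.83 to 1.27 at 30%, if the rate after an event is 0.5 to 1.5 times the rate without one. These figures assume a 1% risk, and the false-significance figures also assume equal groups. The within-cohort analysis and the stated power calculation are untouched. The definition should be changed because the remedy is standard and cheap, not because a particular bias has been shown.

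**What to change.** In Section 9.1:

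- Define unvaccinated controls as members with no influenza vaccine that season up to the index date. Censor them at any later influenza vaccination recorded in KITS, and count an event coded on that same day before censoring.
- Define the IIV and Q/LAIV groups by the product received at the start of follow-up, and censor both at receipt of the other product.

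Minor tidy-up: measure utilization in the 6 months before each subject's own vaccination or index date, and align the prior-year wording in Section 9.7.3 with that definition.

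The cost is a change of wording and one extra date per subject from a database already in use. Controls vaccinated later contribute shorter follow-up, which sampling more controls can offset. If the season-long definition is kept for comparability with the earlier FluMist studies, the index-date definition with censoring should at least be a prespecified sensitivity analysis.

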### 9.2.2 Inclusion Criteria

Subjects must meet *all* of the following criteria:

- 1) Age 2 through 49 years (prior to 50th birthday) at the time of vaccination (or index date for unvaccinated controls)
- 2) Membership in the KP Health Care Plan for at least 12 months prior to vaccination/index date
- 3) Continuous enrollment in the KP Health Care Plan through 6 months following vaccination/index date.

There are no exclusion criteria. Subjects with any high-risk underlying medical condition as defined by ICD-9-CM codes or successor ([Annex 3](#)) will be analyzed separately.

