#### **9.5 Study Size**

Since there are no identified safety concerns with Q/LAIV, this post-marketing safety assessment is hypothesis generating and will include multiple statistical comparisons.

Enrollment of at least 10,000 children 2 through 8 years of age is planned. A sample size of 10,000 children will provide approximately 90% power to observe a statistically significant increase in relative risk (RR) of 1.5 for an event that occurs in 1 in 100 subjects in the comparison group. The study will also be able to rule out with 95% probability the occurrence of an event at a rate of 0.03% (1 in 3,333 subjects) assuming that incidence of the event follows a Poisson distribution. Enrollment is expected to be completed in the 2013-2014 influenza season but the study will be continued for additional seasons, if needed, until enrollment of 10,000 Q/LAIV recipients 2 through 8 years of age is completed to fulfill the postmarketing commitment to the FDA.

However, because the study is expanded to adolescents and adults up to 49 years of age, it is expected that a total of approximately 80,000 individuals will be enrolled (including approximately 10,000 to 30,000 individuals in each of the following 4 age groups: 2 to 4 years, 5 to 8 years, 9 to 17 years, and 18 to 49 years of age) during the 2013-2014 influenza season. Enrollment of 20,000 children per age group will provide approximately 90% power to observe a statistically significant increase in relative risk (RR) of 1.5 for an event that occurs in 1 in 200 subjects in the comparison group. A sample size of 20,000 will also be able to rule out with 95% probability the occurrence of an event with an incidence rate of 0.015% (1 in 6,666 subjects).

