#### **9.7.4.1 Within-cohort Analyses**

Within-cohort analyses will be conducted among Q/LAIV recipients to see if the incidence of safety outcomes is higher within an immediate post-vaccination “risk” period (eg, 0 to 3, 1 to 14, 15 to 42, and 1 to 42 days post vaccination) compared to later “reference” periods, ie, 7 to 9 days post vaccination for the risk period of 0 to 3 days, 43 to 84 days post vaccination for the risk periods of 1 to 14, 15 to 42, and 1 to 42 days.

This will be accomplished in the Cox models by evaluating the main effect of “period,” defined as a time-dependent variable using the counting-process style of data input. Covariates, stratification factors, and the calendar time structure will be incorporated to control for the effects of age, gender, level of health care utilization, and seasonal difference in background event rates. The main effect variable of “period” will compare post-vaccination “risk” periods to “reference” periods occurring after the risk period.

For each study subject, the beginning of each reference period will follow the end of the risk period.

For example:

*riskperiod03*: 1 = risk (Days 0 through 3)

0 = reference (Days 7 through 9)

*riskperiod142*: 1 = risk (Days 1 through 42)

0 = reference (Days 43 through 84)

If specific results from the primary analyses identify a statistically significant increased risk associated with Q/LAIV administration, additional models with main effects structured to compare the “risk” periods to “reference” periods occurring prior to vaccination may be constructed. To reduce the potential bias associated with the “healthy patient effect,” the reference period prior to vaccination would exclude the week immediately prior to vaccination.

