**5.2 Asthma, Recurrent Wheezing, and Active Wheezing**

Children younger than 5 years of age with recurrent wheezing and persons of any age with asthma may be at increased risk of wheezing following administration of FluMist Quadrivalent. FluMist Quadrivalent has not been studied in persons with severe asthma or active wheezing.

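### In the unvaccinated comparison, controls start on an assigned date whatever their current health and respiratory events have no new-event rule, so illness already under way at the index date can bias the hazard ratio downward.

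*Protocol*

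**What the plan says.** **Start of follow-up.** Protocol 9.1: "Unvaccinated controls will be followed from the date of vaccination of the reference Q/LAIV recipient (the index date". Section 9.9 repeats this when it describes how indication bias is to be controlled.

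**Eligibility.** Protocol 9.2.2 asks only for age, prior membership and continued enrollment, and then says: "There are no exclusion criteria". Neither recipients nor controls are screened for acute illness on Day 0.

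**Event counting.** In 9.3 an MAE is any coded diagnosis attached to a medical encounter. Events are discounted for a record in the preceding 12 months only for Guillain-Barré syndrome, Bell's palsy, encephalitis, neuritis, vasculitis and narcolepsy/cataplexy. Table 9.3-1 starts the respiratory and hospitalization windows on Day 1.

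**Adjustment.** Matching is on age and medical center (9.1). The Cox model uses calendar time, with gender and a high/low count of visits over the prior 6 months as covariates (9.1, 9.7.4.2).

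**Healthy patient effect.** Section 9.7.4.1 names it for one optional within-cohort model, to be considered only after a significantly increased risk has appeared. There, "the reference period prior to vaccination would exclude the week immediately prior to vaccination". Section 9.7.4.2, on matched controls, has no counterpart.

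**The concern.** The two groups enter follow-up differently. A recipient's Day 0 is a day on which someone chose to vaccinate. A control's Day 0 is a date borrowed from someone else, so the control may be partway through a bronchitis or pneumonia. Because common respiratory events need not be new, a return visit for that illness is scored as a control event in the first days of the window.

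None of the planned adjustments measures health on the index date. Calendar time handles season, the visit count covers six months in two levels, and the analysis without high-risk subjects removes the Annex 3 conditions, which are mainly chronic.

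Section 9.7.3 declares an increased or a decreased risk from the confidence limits of the adjusted HR. An excess of ongoing illness among controls can therefore keep a true early increase from being declared, or help produce a declared decrease. It also makes the trigger for the optional model in 9.7.4.1 less likely to be met. The early days matter: Annex 4 (package insert, 12.2) reports that the highest proportion of subjects shed vaccine virus on Days 2-3.

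**Working it through.** **1. The plan's own power figure.** Section 9.5: "A sample size of 10,000 children will provide approximately 90% power to observe a statistically significant increase in relative risk (RR) of 1.5". The comparison-group risk behind that figure is 1%. Section 9.7.3: "All statistical tests will be 2-sided and performed at the significance level of 0.05". A two-proportion test with 10,000 per group (1:1 is an assumption, as the ratio is not given), 0.015 against 0.010, has 88.9% power. For 20,000 per group, 0.0075 against 0.005, it is 88.7%. Both agree with the stated figure of about 90%, which is not in dispute.

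**2. Inputs for the bias.** The documents give no rate of ongoing illness, so the following are assumptions:
- New-event risk over Days 1-42: 0.01. This borrows the sizing rate from 9.5. Spread evenly, it is 0.01 × 14/42 = 0.00333 over Days 1-14.
- Length of a coded episode: 7-14 days.
- Ill controls with a coded follow-up visit within 14 days: p = 20%-40%.
- Recipients ill at vaccination: zero, the most unfavorable case.

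**3. Controls ill at index.** Prevalence is about incidence × duration:
- 7 days: q = 0.01/42 × 7 = 0.00167 (0.17%)
- 14 days: q = 0.01/42 × 14 = 0.00333 (0.33%)

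**4. HR when the vaccine has no effect.** Null HR = base/(base + q × p).

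| | q × p | Days 1-42 | Days 1-14 |
|---|---|---|---|
| Low (7 days, 20%) | 0.000333 | 0.01/0.010333 = 0.97 | 0.00333/0.003667 = 0.91 |
| High (14 days, 40%) | 0.001333 | 0.01/0.011333 = 0.88 | 0.00333/0.004667 = 0.71 |

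**5. What happens to a true RR of 1.5.** Multiplying by the null HR:
- Days 1-42: 1.5 × 0.968 = 1.45 to 1.5 × 0.882 = 1.32
- Days 1-14: 1.5 × 0.909 = 1.36 to 1.5 × 0.714 = 1.07

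With 10,000 per group over Days 1-42, the test from step 1 with the control risk raised to 0.010333 or 0.011333 (recipients at 0.015) has power 83.9% or 62.3%, against 88.9% without the bias.

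**6. False declaration of a decreased risk.** With no vaccine effect, recipients at 0.010 and controls at 0.010333 or 0.011333, the same test finds a significant decrease with probability 4.2% or 14.9%. The nominal value is 2.5% in that direction.

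**The case against.** **Recipient fitness is inferred.** No passage requires recipients to be well, and the absence of exclusions applies to them too. The package insert says "FluMist Quadrivalent has not been studied in persons with severe asthma or active wheezing", but that is a warning; its contraindications concern severe allergy and aspirin. A reader might infer that every recipient was fit on Day 0. The documents support only a tendency, through the protocol's own mention of the healthy patient effect.

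**Net direction.** Section 9.1 expects the groups to differ in health-seeking behavior. If unvaccinated members seek less care, they generate fewer coded visits, which pushes the HR up. A two-level visit covariate controls this only partly. This stands: the mechanism described here acts downward, but the sum of all biases is unknown.

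**The worst-affected window.** Section 9.7.4.2 gives its windows for matched controls as examples (0-3, 1-42 and 1-180 days) and does not name Days 1-14. Table 9.3-1 does list Days 1-14, so the window is not ruled out, but the larger figures should carry that caveat.

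**Other safeguards.** IIV controls were also selected for vaccination and largely share this selection. Sections 9.1 and 9.9 admit differences in health status and indication bias, and the study is described as hypothesis generating. These limit the consequences without correcting the unvaccinated HR. The within-cohort analysis avoids these controls, but recipients who are unusually well at first would lower its early window as well.

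**Is this a matter for the SAP?** Detailed episode rules often belong there. However, the protocol itself fixes the start date, the absence of exclusions and the list of diagnoses with a prior-record rule.

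**Conclusion.** The point holds as a possible downward bias in the unvaccinated comparison for lower respiratory MAEs, wheezing MAEs and hospitalizations. It does not extend in the same way to the IIV comparison.

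Under the stated assumptions the null HR is about 0.97-0.88 for Days 1-42 and 0.91-0.71 for Days 1-14. These ranges rest on an evenly spread 1% risk, 7-14 day episodes, 20%-40% of ill controls returning, and no recipients ill at vaccination. If some recipients are also ill, the effect is smaller. For hospitalizations the documents give no basis for a figure.

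Two stronger readings are not supported. One is that the design does hide early harm; the documents show only that it can. The other is a much larger effect. Supposing 1% more controls than recipients are ill at index, with 40% returning, would give 0.01/0.014 = 0.71 for Days 1-42 and 0.00333/0.00733 = 0.45 for Days 1-14. With a 1% risk over 42 days, however, a 1% prevalence needs episodes averaging 0.01/(0.01/42) = 42 days, which does not fit acute respiratory illness.

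This is an inexpensive improvement. It does not invalidate the study.

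**What to change.** In 9.7.4.2, for the unvaccinated comparison, add one rule applied identically to both groups:
- Count a lower respiratory MAE, a wheezing MAE or a respiratory hospitalization only in subjects with no encounter of the same category in Days -7 to -1. Leave the other subjects out of both the events and the person-time for that outcome.
- For any hospitalization, leave out subjects already in hospital on Day 0.
- Report each result with and without the rule, and interpret any HR below 1 in that light.

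The one-week span matches the week that 9.7.4.1 already treats as affected, although there it removes reference time and here it removes subjects. The look-back data are available because 9.2.2 requires 12 months of prior membership.

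The cost is a paragraph of text and one filter on encounter data already held. Some subjects are lost, probably few, and the restricted result describes people without a recent respiratory episode; the unrestricted result preserves the routine-practice population. The rule reduces the bias without removing it, since an episode with no coded visit in that week passes through.
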